6.4. VISIT WINDOWS

There will be no derivation for visit windows in terms of summary of assessments. Nominal visits as indicated in Table 1 will be used for TLFs.

6.5. POOLING OF CENTERS

There will be no pooling of centers.

Statistical Analysis Plan
Final V1.0

[name], Ltd.
Protocol #DFN-02-CD-012
INC Research #1007752

7. DEMOGRAPHIC, OTHER BASELINE CHARACTERISTICS AND MEDICATION

7.1. SUBJECT DISPOSITION AND WITHDRAWALS

Subject disposition will be presented for the Screened Set, and will include the following:

- The number of subjects screened
- The number of subjects who failed screening
- The number of subjects randomized into DB1
- The number of subjects re-randomized into DB2
- The number (%) of subjects in the FAS1
- The number (%) of subjects in the FAS2
- The number (%) of subjects in the SS
- The number (%) of subjects in the PPS
- The number (%) of subjects who completed DB1
- The number (%) of subjects who completed DB2
- The number (%) of subjects who completed the study
- The number (%) of subjects who discontinued from DB1 and the primary reason for discontinuation
- The number (%) of subjects who discontinued from DB2 and the primary reason for discontinuation
- The total number (%) of subjects who discontinued from the study and the primary reason for discontinuation

The summary will be performed for the Screened Set, as well as for the DB1 and DB2 treatment periods. The denominator for the Screened Set overall portion will be the total number of screened subjects. The denominator for the DB1 portion will be the number of subjects in the randomized set for DB1. The denominator for the DB2 portion will be the number of subjects in the randomized set for DB2. No statistical testing will be performed on these data.

Subjects' completion/discontinuation status will be listed, including subject identifier, date of completion/early discontinuation and, for those who discontinued early, the specific reason(s) for discontinuation.

The inclusion/exclusion criteria for the subjects who fail screening will be listed. All protocol deviations will be listed.

7.2. DEMOGRAPHIC AND OTHER BASELINE CHARACTERISTICS

Demographics and other baseline characteristics will be summarized for the SS, SS1, and SS2 by treatment group and overall, with descriptive statistics including n, mean, standard deviation, median, minimum, and maximum for numeric variables and frequency and percentage for categorical variables. Demographics include age, gender, childbearing potential for females, ethnicity, race, height, weight, smoking history, and body mass index (BMI).

BMI will be calculated as follows:

$$\text{BMI (kg/m}^2\text{)} = \text{Weight (kg)} / [\text{Height(m)}^2].$$

All collected demographics and baseline characteristics will be listed.

7.3. MIGRAINE HISTORY

All migraine history data will be summarized descriptively by treatment group and overall for the SS, SS1, and SS2.

All collected migraine history data will be listed.

7.4. MEDICAL HISTORY AND CONCOMITANT DISEASES

A summary table of the number and percentage of subjects by medical history system organ class (SOC) and preferred term (PT) will be produced for subjects in the SS. Previous and concurrent diseases/conditions will be sorted alphabetically by SOC and PT using the Medical Dictionary for Regulatory Activities (MedDRA) coding dictionary, version 19.0 or higher. For the summary tables, a subject may appear more than once if he/she has more than one medical history coded under different SOC categories. However, the subject will be counted only once in the overall category.

A separate by-subject listing for medical history data will also be provided. Surgical history including procedure, date of surgery, and reason for surgery will be listed.

7.5. MEDICATION

7.5.1. Study Medication Accountability

All data in the study medication accountability log will be listed, which will include the dates and kit number(s) of the medication dispensed and returned.

Statistical Analysis Plan

Final V1.0

[name], Ltd.
Protocol #DFN-02-CD-012
INC Research #1007752

7.5.2. Prior and Concomitant Medications

All prior and concomitant medications will be classified using the Anatomical Therapeutic Chemical (ATC) classification and preferred drug names from the World Health Organization Drug Dictionary (WHO-DD), version March 2016.

Summaries of medications will be presented in tabular form using the highest level ATC term as an upper classification and the preferred drug name as a lower classification level. All medications will be summarized by dose level and sorted by descending counts in the upper classification term and the lower classification term within the upper. The summary will consist of the frequency and percentage of subjects who used the medication at least once. For each subject, the medication will be counted only once within the upper classification level and only once within the lower classification level.

Medications will be considered prior if stopped before the DB1 dose date. Medications with a start or stop date on or after the DB treatment period dosing date will be considered concomitant medications. If a concomitant medication starts on or after the start time of DB1 dose administration, it is considered a concomitant medication to the study treatment in DB1, but not in DB2. If a concomitant medication starts on or after the start time of DB2 dose administration, it is considered a concomitant medication to the study treatment in DB2. All medications marked as ongoing are concomitant medications. A medication with an incomplete start/stop date will have its date imputed as described in SAP Section 6.3 solely to determine if the medication is prior or concomitant.

Summaries of prior and of concomitant medications will be presented separately in tables and will be based on the SS. Prior and concomitant medications will be listed by subject. An identifier will be included to show if a medication is prior or if it is concomitant with respect to the applicable DB treatment period.

Statistical Analysis Plan
Final V1.0

[name], Ltd.
Protocol #DFN-02-CD-012
INC Research #1007752

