11.6.6 Safety Analysis

All AEs will be coded using the latest version of the Medical Dictionary for Regulatory Activities (MedDRA) version 19.0 or higher. A TEAE is an AE with a start date on or after the initial dose of study medication and up to 5 days after the last dose of study medication. Only TEAEs will be included in summary tables. Migraine headaches will not be captured as AEs. Migraine headaches will be captured by the patient in the eDiary provided to them at screening. The information will then be entered into the appropriate eCRF page.

The incidence of all TEAEs will be tabulated by treatment received. These TEAEs will be classified by system organ class (SOC) and preferred term (PT). For incidence reporting, if a patient reported more than one AE that was coded to the same SOC or PT, the patient will be counted only once for that specific SOC or PT.

An overview of AEs, which includes patient incidence of TEAEs, headache or migraine-related TEAEs, study medication-related TEAEs, and SAEs, will be presented. The patient incidence of TEAEs, headache- or migraine-related TEAEs, study medication-related TEAEs, and SAEs will be summarized by SOC and PT.

CONFIDENTIAL

Treatment-emergent adverse events will also be summarized in a table by severity. For TEAEs presented by severity, the worst severity during the study will be presented for each patient, SOC, and PT.

Treatment-emergent adverse events will also be summarized in a table by relationship to study medication. For TEAEs presented by relationship to study medication, the strongest relationship to study medication during the study will be presented for each patient, SOC, and PT.

All AEs will also be presented in a by-patient data listing.

All prior and concomitant medications will be classified using the Anatomical Therapeutic Chemical (ATC) classification and preferred drug names from the World Health Organization Drug Dictionary (WHO-DD), version March 2016 or later. Medications will be considered concomitant if they were taken at any time between the date of first dose and the date of last dose of study medication, inclusive. Medications will be considered as prior if stopped before the date of first dose of study medication during the DB1 treatment period.

Prior and concomitant medications will be summarized in separate tables by ATC level 2 and preferred drug name for the safety population.

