6. GENERAL ASPECTS FOR STATISTICAL ANALYSIS

6.1. GENERAL METHODS

6.1.1. Summary Statistics

In general, descriptive statistical methods will be used to summarize the data from this study. With appropriate sample sizes, hypothesis testing can be performed for the primary and secondary efficacy endpoints.

The term "treatment group" refers to the applied treatment regimen during DB1 or DB2 (DFN-02 10 mg or placebo). All data collected during the study will be included in subject data listings. All subjects entered into the database will be included in subject data listings. Unless otherwise noted, the data will be sorted first by treatment group, subject number, and then by date within each subject number.

Unless stated otherwise, the term "descriptive statistics" refers to number of subjects (n), mean, median, standard deviation, minimum, and maximum for continuous data and frequencies and percentages for categorical data.

All categorical/qualitative data will be presented using absolute frequency counts and percentages. The total number of subjects in the treatment group overall (N) in the specified population will be used as the denominator for percentage calculations, unless stated otherwise in the table shell. All percentages will be presented in parentheses with 1 decimal point, unless otherwise specified. Percentages equal to 100 will be presented as 100% and percentages will not be presented for zero frequencies.

Unless specified otherwise, all statistical testing and confidence intervals (CIs) will be 2-sided and will be performed using a significance (alpha) level of 0.05.

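### SAP 7.5.2 labels a drug started between the two doses and still in use at the DB2 dose as concomitant with DB1 only, contradicting its own general rule; the effect is confined to descriptive medication outputs

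*SAP*

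**What the plan says.** SAP 7.5.2 gives a general definition of a concomitant drug, then two sentences that assign such drugs to a period.

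- General definition: "Medications with a start or stop date on or after the DB treatment period dosing date will be considered concomitant medications". Either date can qualify a drug, and the test is tied to the dosing date of a period.
- DB1 sentence: "If a concomitant medication starts on or after the start time of DB1 dose administration", then "it is considered a concomitant medication to the study treatment in DB1, but not in DB2". Only the start time counts.
- DB2 sentence: it opens "If a concomitant medication starts on or after the start time of DB2 dose administration" and assigns such drugs to DB2. Again only the start time counts.
- Ongoing drugs: "All medications marked as ongoing are concomitant medications". No period is named.
- Listing: "An identifier will be included to show if a medication is prior or if it is concomitant with respect to the applicable DB treatment period". The period label is therefore a specified output.

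The same section bases the prior and concomitant medication tables on the Safety Set (SS). The index of tables has one concomitant medication table, 14.1.4.2, on the SS, and no SS1 or SS2 version.

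Protocol 11.6.6 defines concomitant by use over the whole dosing span: "Medications will be considered concomitant if they were taken at any time between the date of first dose and the date of last dose". It has no period rule. Protocol 11.1 lets the SAP prevail where the two differ. SAP section 11, which lists departures from the protocol analysis, has no entry for 7.5.2.

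**The concern.** Whether a drug accompanies a dose depends on whether it was in use around that dose, not only on when it was started. A start-time rule fails for a drug begun after the DB1 dose and still taken at the DB2 dose. It was not in use when the DB1 dose was taken and was in use when the DB2 dose was taken, yet it is labelled DB1 and expressly not DB2.

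DB2 is re-randomized and has its own safety set and its own window for treatment-emergent events (SAP 5.3, 6.2.5). Someone reading a DB2 adverse event against the medication listing would see a DB1 label on a drug the subject was taking at the DB2 dose. Because the general sentence points the other way, two programmers could also derive different labels from the same record.

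**Working it through.** There is no stated figure to reproduce. The check applies each sentence to test cases.

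**Time available for such drugs.** The SAP (3.4) allows 2 to 7 days to return after a treated attack and up to 4 weeks in each period to treat one. If visits keep to those windows, the gap between the DB1 and DB2 doses runs from about 2 days to about 7 + 28 = 35 days. A drug can be started in that gap and continue past it.

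**Assumed dosing days.** DB1 dose on day 1 and DB2 dose on day 29. Only the order of events matters to the result.

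**Rules applied.**
- Period sentences: start on or after day 29 gives DB2; start from day 1 to day 28 gives DB1 only; an earlier start is given no period. This reads the DB2 sentence as overriding the DB1 sentence from day 29, although the DB1 sentence has no upper limit.
- General sentence, read period by period: start or stop on or after that period's dosing day.
- In use on the dosing day: start ≤ dosing day ≤ stop, with no stop for ongoing drugs.

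| Case | Use | Period sentences | General sentence | In use on dosing day of |
|---|---|---|---|---|
| a | Day 3, ongoing | DB1 only | DB1 and DB2 | DB2 |
| b | Day 25 to 40 | DB1 only | DB1 and DB2 | DB2 |
| c | Day 3 to 10 | DB1 only | DB1 | Neither |
| d | Day 29 to 35 | DB2 | DB1 and DB2 | DB2 |
| e | Before DB1, ongoing | None named | DB1 and DB2 | Both |

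**Results.**
1. Cases a and b show the fault: in use only at the DB2 dose, labelled DB1 and not DB2. The general sentence puts both in DB2 as well.
2. The ongoing sentence makes case a concomitant but names no period, so it does not restore the DB2 label.
3. Case c is labelled sensibly by both.
4. In case d the general sentence adds DB1 to a drug first taken at the DB2 dose, so the general sentence alone is not a clean period rule either.
5. Case e gets a period only from the general sentence.
6. All five drugs are concomitant overall under Protocol 11.6.6. The difficulty lies in the period label that the SAP adds.

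**Reach of the label.** The SAP specifies it for the by-subject listing. For the table, SAP 6.1.2 presents summaries by treatment unless otherwise specified, and under SAP 6.1.1 treatment group "refers to the applied treatment regimen during DB1 or DB2 (DFN-02 10 mg or placebo"), so one subject can belong to both groups. The SAP does not say which column of the SS table receives a drug taken by a subject who had both treatments, or that the period label decides it. The efficacy exclusions in SAP 8.1.1 and 8.2 depend on a second dose or rescue by the 2-hour assessment, and rescue medication has its own definition, tables and per-period listings (SAP 9.2). None of these uses the label.

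**The case against.** The strongest reply is that this is a wording conflict in a descriptive display. The affected drug stays concomitant and stays in the listing; it lacks only a DB2 label. The general sentence could also be read as defining concomitant overall, with the next two sentences allocating periods. Much of this stands, but that reading removes the contradiction only by leaving the DB1-only rule in force, so cases a and b remain mislabelled.

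The protocol also limits how often such drugs should arise. Section 9.5.3 bars starting SSRIs, SNRIs, tricyclics or chronic steroids during the study, and prohibits short-term use. Concomitant medication and eligibility are reviewed at Visit 3. Section 9.5.2 restricts taking the first dose within 48 hours of acute migraine treatment or an analgesic. These limits reduce the number of cases but do not remove them: 9.5.3 allows newly prescribed drugs with the Investigator's agreement, and deviations can occur.

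A reader might infer three stronger claims that the documents do not support.

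- **Every drug started after the DB1 dose loses its DB2 label.** The DB2 sentence assigns drugs started on or after the DB2 dose to DB2. Those at issue started between the doses and were still in use at the DB2 dose.
- **About half of these drugs are counted in the wrong arm.** Under independent 1:1 allocation in both periods, the arms differ with probability 2 × 0.5 × 0.5 = 0.5. That describes arm changes, not table errors. It becomes a misattribution rate only if the SS table uses the period label, which is not stated. Independence is itself an assumption, since Protocol 9.1 also speaks of treatment sequences.
- **The label biases the DB2 efficacy comparison.** No described efficacy analysis uses it.

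Nor does the SAP reverse a protocol rule on periods: the protocol has none.

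**Conclusion.** The concern holds as a labelling error with limited reach. Read literally, SAP 7.5.2 gives the wrong period identifier to any drug started between the two doses and still in use at the DB2 dose, and the general sentence in the same paragraph gives a different answer. Because the SAP prevails over the protocol and section 11 is silent, nothing elsewhere in the documents corrects it.

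The listing error follows directly from the text. Misattribution in the SS table is possible but conditional on an unstated column rule. Primary and secondary efficacy tests, power and alpha are unaffected. The number of drugs involved cannot be estimated from the documents. The conclusion assumes that the DB1 sentence is programmed as written and that the DB2 sentence governs drugs started on or after the DB2 dose.

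**What to change.** Replace the two period sentences in SAP 7.5.2 with an overlap rule:

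- Concomitant in DB1: started before the DB2 dose (or at any time if there was no DB2 dose), and ongoing or stopped on or after the DB1 dose.
- Concomitant in DB2: ongoing or stopped on or after the DB2 dose, whatever the start date.
- A drug may belong to both periods.

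Applied to the test cases, this gives DB1 and DB2 for a, b and e, DB1 only for c, and DB2 only for d. Rescue for the DB1 attack that stopped before the DB2 dose stays in DB1. A drug begun shortly before the DB2 dose keeps a DB1 label, because DB1 is taken to run until the DB2 dose, but it now carries the DB2 label too.

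State that the SS table attributes each drug to the treatment of every period in which it is concomitant. Align the general sentence with the new rule, and list the change in SAP section 11.

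The cost is a few sentences of SAP text and one derivation, with no new data. Some drugs will appear under both periods and, for subjects who changed treatment, under both treatment columns; a table footnote should say so.

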8. EFFICACY

8.1. PRIMARY EFFICACY ENDPOINT AND ANALYSIS

8.1.1. Primary Analysis of the Primary Endpoint

The primary efficacy endpoint is the proportion of subjects who are free from headache pain at 2 hours after the first dose of study medication taken for a migraine attack with moderate to severe headache pain during the DB1 treatment period (ie, headache pain rating of moderate [Grade 2] or severe [Grade 3] predose reduced to none [Grade 0] at 2 hours postdose). The primary efficacy endpoint will be analyzed using Fisher's exact test.

Proportions of subjects free from headache pain at 2 hours postdose will be calculated as the number of subjects who are pain-free at 2 hours postdose divided by the number of subjects with non-missing assessment at 2 hours postdose. Missing primary efficacy endpoint data will be imputed using the last observation carried forward (LOCF). Results based on the LOCF data and the observed data will be displayed separately.

The number of subjects with response, the number of subjects with non-missing assessment, proportions for the DFN-02 10 mg and placebo groups, 95% exact CIs for those proportions, the odds ratio for response, and the corresponding p-value will be presented for the comparison between two treatment groups for the FAS1. This analysis will exclude subjects who took a second dose of study medication or rescue medication prior to the data collection of the 2 hours postdose time point (inclusive). The analysis will also be performed using the PPS.

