11.6 Methods of Analysis

11.6.1 Primary Efficacy Analysis

Efficacy analysis for primary, secondary, and exploratory endpoints will be based on the FAS population.

The primary efficacy endpoint, the proportion of patients who are free from headache pain at 2 hours after the first dose of study medication taken for a migraine attack with moderate to severe headache pain during the DB1 treatment period, will be analyzed using Fisher's exact test. The response rate will be calculated as the number of patients who are pain-free at 2 hours postdose divided by the number of patients with non-missing assessment at 2 hours postdose. The number of patients with non-missing assessment, the number of patients with response, the response rate, and the p-value for comparing DFN-02 10 mg versus placebo will be presented.

Analysis will be performed using the last observation carried forward (LOCF) and observed data in the FAS population and PP population.

Additional sensitivity analyses and data handling rules for missing data of the primary endpoint will be documented in detail in the SAP.

CONFIDENTIAL

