11.8 Determination of Sample Size

One hundred patients will be randomized for the DB1 treatment period. Patients who discontinue participation without completing the study protocol will not be replaced.

The primary endpoint is the comparison of the proportion of patients who are pain-free at 2 hours after the first dose of study medication. It is assumed that 15% of placebo and 42% of DFN-02 (treated) patients will be pain-free at 2 hours. A sample size of 50 patients in each DB1 dosing arm will provide 81% power to detect this assumed difference between placebo and DFN-02 at a 5% (2-sided) level of significance.

12 Quality Assurance and Quality Control

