3.6. DETERMINATION OF SAMPLE SIZE

Approximately 100 subjects will be randomized for the DB1 treatment period. Subjects who discontinue participation without completing the study protocol will not be replaced.

The primary endpoint is the comparison of the proportion of subjects who are pain-free at 2 hours after the first dose of study medication. It is assumed that 15% of placebo and 42% of DFN-02 10 mg (treated) subjects will be pain-free at 2 hours. A sample size of 50 subjects in each DB1 dosing arm will provide 86% power to detect this assumed difference between placebo and DFN-02 10 mg at a 5% (2-sided) level of significance.

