¹³ Screening eDiary information will be kept in the source document. It is compulsory for all the subjects to check-in the eDiary every day during the entire study period. If a subject does not check-in consistently or does not report a migraine attack in the eDiary for 2 to 3 weeks, it is recommended they should be contacted by study staff to check if the subject has technical difficulties or confirm they have not experienced a migraine.

¹⁴ Arrangements should be made by the site for a timely return of the eDiary device for subjects who screen fail.

Statistical Analysis Plan

Final V1.0

[name], Ltd.
 Protocol #DFN-02-CD-012
 INC Research #1007752

Table 2 eDiary Assessments

	Randomization	Predose Baseline	Postdose				
			10, 15, 20, 30 min	1 h	1.5 h	2 h	24 h
Migraine start and aura information, study medication, and non-study medication taken for migraine attacks dosing			As applicable ¹				
Time to meaningful pain relief			As applicable up to 2 hours postdose				
Time to pain freedom			As applicable up to 2 hours postdose				
Pain level ²		X	X	X	X	X	X
Functional disability ³		X				X	X
Presence of nausea/photophobia/phonophobia [REDACTED]		X	X	X	X	X	X
Most bothersome symptom (selected between nausea, photophobia and phonophobia) ⁴		X					
PPMQ-R	X						X
Subject treatment satisfaction (7-point scale) ⁵						X	
Abbreviations: h = hour(s); min = minutes; PPMQ-R = Patient Perception of Migraine Questionnaire-Revised							
¹ End of migraine pain, and non-study medication use may occur more than 24 hours postdose.							
² Pain levels: 0 = none; 1 = mild; 2 = moderate; 3 = severe							
³ Functional disability scale: 0 = no disability, able to function normally; 1 = performance of daily activities mildly impaired, can still do everything but with difficulty; 2 =							

Statistical Analysis Plan

Final V1.0

[name], Ltd.
Protocol #DFN-02-CD-012
INC Research #1007752

performance of daily activities moderately impaired, unable to do some things; 3 = performance of daily activities severely impaired, cannot do all or most things, bed rest may be necessary

⁴ The most bothersome symptom will be collected only if more than 1 symptom is present predose; if only 1 symptom is present, it will be considered the most bothersome.

⁵ Treatment satisfaction baseline for the migraine medication to be collected prior to randomization in the PPMQ-R.

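### Cheap improvement, not an error: the primary Fisher's exact test is valid but conservative, and a test stratified by predose pain grade, or Boschloo's test, would recover about 3 to 7 points of power

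*SAP*

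**What the plan says.** On the test, SAP 8.1.1 reads: "The primary efficacy endpoint will be analyzed using Fisher's exact test". Protocol 11.6.1 names the same test and says that "the p-value for comparing DFN-02 10 mg versus placebo will be presented". Neither section names a stratum or covariate, and neither Protocol 9.1.2 nor SAP 3.7 names a stratification factor for randomization.

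On the estimate, SAP 8.1.1 adds that "95% exact CIs for those proportions, the odds ratio for response, and the corresponding p-value will be presented". The intervals are for the two response proportions. None is specified for the odds ratio or for the difference between arms.

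On power, SAP 3.6 says: "It is assumed that 15% of placebo and 42% of DFN-02 10 mg (treated) subjects will be pain-free at 2 hours". It continues: "A sample size of 50 subjects in each DB1 dosing arm will provide 86% power". Protocol 11.8 has the same rates and significance level but says: "A sample size of 50 patients in each DB1 dosing arm will provide 81% power".

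On predose grade, the eDiary table in SAP 3.9 lists pain level as a predose item, with the footnote "Pain levels: 0 = none; 1 = mild; 2 = moderate; 3 = severe". The primary endpoint is defined as a change from grade 2 or 3 to grade 0, so the grade is already part of its derivation. Two provisions limit its use as a stratum. Protocol 10.2.1.2 and 10.2.1.4.1 allow predose entries to be made retrospectively. The FAS1 definition in SAP 5.4 does not require a predose grade of 2 or 3.

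**The concern.** Fisher's test conditions on the total number of responders. With 50 per arm that leaves few attainable p-values, so the rejection region falls well short of 5%. The unused significance level is lost power. The SAP states a power that its own named test does not reach. The margin is also thin: dropouts are not replaced, the sample size carries no allowance for them, and SAP 8.1.1 excludes subjects who take an early second dose or rescue medication.

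The analysis also makes no use of a baseline grade that is collected anyway. What is at stake is efficiency and a usable effect estimate with its precision, not the validity of the p-value.

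**Working it through.** **Inputs.** 50 per arm, 15% v 42%, two-sided 5% (SAP 3.6, Protocol 11.8); Fisher's exact test (SAP 8.1.1, Protocol 11.6.1). The documents give neither the share of severe attacks nor the effect of grade on pain freedom. Assumed here: 30-50% severe, and a moderate-v-severe odds ratio for pain freedom of 1 to 4, with marginal rates held at 15% and 42%.

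**1. The SAP's 86%.** Pooled normal approximation without continuity correction:
- mean rate = (0.15 + 0.42)/2 = 0.285
- SE under the null = √(2 × 0.285 × 0.715/50) = 0.0903
- SE under the alternative = √((0.15 × 0.85 + 0.42 × 0.58)/50) = 0.0862
- power = Φ((0.27 − 1.96 × 0.0903)/0.0862) = Φ(1.08) = 86.0%

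The figure reproduces, but it is not the power of Fisher's test.

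**2. The Protocol's 81%.** Sum the product of the two binomial probabilities over all 51 × 51 tables with two-sided Fisher p ≤ 0.05. At 15% v 42% this gives 81.7%. The normal approximation with continuity correction gives 80.2%. The Protocol's figure is therefore in line with the named test; the SAP's is about 4 points too high for it.

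**3. True size of Fisher's test.** The same sum with a common rate in both arms:

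| Common rate | 15% | 20% | 25% | 28.5% | 35% | 42% |
|---|---|---|---|---|---|---|
| Size | 2.39% | 2.82% | 3.02% | 3.07% | 3.04% | 3.31% |

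The maximum over all rates is 3.52%, at 50%.

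**4. Boschloo's test.** It uses Fisher's p-value as the statistic and sets the cut-off so that the maximum size stays at or below 5%. Power is 84.7%, a gain of 2.9 points, with maximum size 4.9%. It rejects every table that Fisher's test rejects, so it is never less powerful.

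**5. CMH test by predose grade, no continuity correction.** Simulation with 100,000 trials per scenario, Monte Carlo error about 0.1 point:

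| Odds ratio, moderate v severe (assumed) | Power |
|---|---|
| 1 | 86.3-86.4% |
| 2 | about 86.9-87.0% |
| 3 | 87.6-88.0% |
| 4 | 88.1-88.9% |

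Simulated size is 4.8-5.0% at common rates of 15% and 28.5%; further runs with 40-50 per arm gave at most 5.2%. With the continuity correction, power is only 80.4-83.5%, and most or all of the gain is lost.

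**6. Where the gain comes from.** If grade is not prognostic, the gain is 86.3 − 81.7 = about 4.5 points, all from removing the conservatism. The most that grade adds is 88.9 − 86.4 = 2.5 points, at an odds ratio of 4.

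**7. Fewer evaluable subjects.** At 48 per arm, Fisher's test has 79.5% power and Boschloo's 82.7%. At 45 per arm the figures are 76.2% and 82.4%. The gap depends on the exact arm sizes; at 47 and 46 it is only 1.3 points.

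**The case against.** The case for leaving the plan alone is a good one. Fisher's test is pre-specified, identical in both documents and guaranteed not to exceed 5%. The Protocol's 81% already reflects it. In a Phase 2 trial of about 100 patients, a test with guaranteed size is a defensible choice. All of this stands, and it is why the point is an improvement and not an error.

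The case for grade is weaker than it may look. Against an uncorrected chi-square test (86.8% power, though with size up to 5.5% over the planned rates), stratifying costs about 0.5 point at an odds ratio of 1 and adds at most about 2 points at the strongest assumed effect. The stratum is also not perfectly clean, since predose grades may be entered late and FAS1 can contain subjects whose grade is missing or mild. CMH rests on a large-sample approximation. These objections stand as well. The fix must therefore switch off the continuity correction and state a rule for the grade. A sponsor who wants guaranteed size has Boschloo's test, which needs neither the grade nor the approximation.

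None of this answers two remaining points: the SAP's 86% is not the power of its own test, and no interval is specified for the treatment effect.

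**Conclusion.** The primary test is valid but conservative: true size 2.4-3.3% over the planned rates and 81.7% power, against the 86% that SAP 3.6 states. The exact results for Fisher's and Boschloo's tests rest only on the documents' own inputs. At the same sample size, Boschloo's test gains 2.9 points and uncorrected CMH about 4.5 points with no assumption that grade matters. The upper end, about 7 points (88.9 − 81.7), needs an assumed odds ratio of 4 between grades.

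Three stronger readings are tempting and are not supported:
- **That the test is wrong or threatens the type I error.** Its size is below 5%, so the error is on the safe side.
- **That ignoring grade is what costs up to 7 points.** Most of the loss comes from the conservatism. Grade accounts for 0 to 2.5 points, and the documents give no figure for its effect.
- **That chance imbalance in severe attacks biases the estimate.** With 50% severe, the SD of the imbalance is √(2 × 0.5 × 0.5/50) = 10 percentage points. An imbalance of that order moves the risk difference by only about 1.1-1.3 points at an odds ratio of 2 and 2.0-2.4 at 4. The standard error is about 8.6 points, and a randomized comparison already allows for chance imbalance of this kind.

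**What to change.** Before unblinding, amend SAP 8.1.1 as follows:
1. Make the primary test a CMH test stratified by predose pain grade (2 v 3), explicitly without continuity correction.
2. State how subjects with a missing predose grade, or one other than 2 or 3, enter the analysis, and whether a retrospectively entered grade is used. The blinded data review in Protocol 11.1 is a natural place to settle this.
3. Report the common odds ratio and the stratified risk difference, each with a 95% confidence interval.
4. Keep Fisher's test as a supportive analysis.
5. Restate the power in SAP 3.6 for the test chosen; for Fisher's it is about 82%, not 86%.

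If guaranteed size or independence from grade is preferred, name Boschloo's exact test instead and add an interval for the risk difference. Choose one primary test; do not leave both open.

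The cost is a few SAP lines and a few lines of code, with no new data. The downside of CMH is its large-sample approximation and the need for the grade rule. Once the data are unblinded, Fisher's test should stay primary, and any stratified result should be labelled post hoc.
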